11.4.3 Exploratory safety biomarkers

Serum biomarkers ([REDACTED]),
[REDACTED] only in subjects with severe headache and/or moderate to severe GI

disturbance) will be listed by treatment group and time point including changes from Baseline. Descriptive summaries (including n, arithmetic mean, median, SD, minimum and maximum) will be presented by treatment group and time point for both absolute values and changes from Baseline.

Mean and mean change from Baseline values will be plotted over time by treatment group with all treatment groups overlaid on the same plot and separate plots for each variable.

Any values that are BLQ or ALQ will be handled as described in [Section 4.2.2](#).

11.4.4 Physical examination

Results of physical examination will be listed.

11.4.5 Other safety variable

Results of interferon-gamma release assay (IGRA) tuberculosis test will be listed.

Results of Serum pregnancy test will be listed.

Results of tuberculosis signs and symptoms questionnaire will be listed.

Results of serology testing for human immunodeficiency virus (HIV), Hepatitis B and Hepatitis C will be listed.

Suicidal ideation will be queried according to the scheduled in table 5.1 of the CSP. A full Columbia Suicide Severity Rating Scale (C-SSRS) assessment will be performed only when subject has a positive response to the suicidal ideation query. Results of suicidal ideation and C-SSRS will be listed.

Full Neurological examination will be performed at screening and at Visit 9 (Day 29). Brief neurological examination will be performed at Visit 2 (Baseline) and Visit 9 (day 29). Results of the neurological examinations will be listed.

12 OTHER ANALYSES

Vaccination-specific antibody titres (██████████) will be listed.

Subjects experiencing severe headache will complete the Headache Questionnaire and will complete the questionnaire daily until resolution (ie, if headache becomes moderate or mild, normal collection of AEs should apply); this assessment will be followed by a neurological assessment (including fundoscopy). Further workup will be performed (if indicated) at the discretion of the investigator and may include, eg, a computed tomography (CT) scan, magnetic resonance imaging (MRI) and/or a lumbar puncture (LP) for cerebral spinal fluid (CSF) collection. In addition assessment of exploratory safety biomarkers should be performed for subjects experiencing severe headache. These investigations will be performed in order to further understand the mechanism of headache in these subjects.

The results of the headache questionnaire, neurological examination and any additional tests performed (CT scan, fundoscopy and LP for CSF collection) will be listed for each subject. No summary tabulations will be provided for these assessments

Stool collection and analysis will be performed for subjects reporting moderate or severe diarrhea. Results of the analysis will be listed for each subject. No summary tabulation will be provided this assessment.

Subject's body weight will be listed and summarized over all treatment groups.

This document cannot be used to support any marketing authorization application and any extensions or variations thereof.

REDACTED COPY

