12.3.4 Body weight and height

The subject's body weight (without shoes) will be determined at Screening (Visit 1), Visit 9, and at the FV (Visit 20). Height will be measured at Screening (Visit 1) only.

Physical examination 12.3.5

Physical examination (full or brief) will be performed at visits as specified in the schedule of study assessments (Table 5.1) and findings will be recorded in the eCRF.

Clinically important abnormal changes in subsequent physical examinations will be recorded as AEs. Physical examinations must be documented in source documentation.

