It is expected that subjects will receive treatment as randomized and hence safety analyses will be based on the randomized treatment group. However, if after unblinding it is determined that a subject has received the incorrect treatment based on the randomization schedule, then for safety analyses the subject will be allocated to the actual treatment they received in the respective Dosing Period.

Full Analysis Set:

The Full Analysis Set (FAS) will consist of all subjects in the SS, who have a Baseline and least 1 post-Baseline QMG measurement during Dosing Period 1 (up to and including Visit 9, ie, Day 29).

The FAS is the primary analysis set for efficacy analyses. As for the SS, in the case of mistreatment, subjects will be primarily analyzed as treated. However, if applicable, sensitivity analysis will also be performed according to the randomized treatment group.

Per-Protocol Set:

The Per-Protocol Set (PPS) is a subset of the FAS, consisting of those subjects who had no important protocol deviations affecting the primary efficacy variable, as confirmed during a pre-analysis data review meeting conducted prior to study unblinding. Post-Baseline deviations will not necessarily lead to total exclusion of a subject from the PPS but may lead to exclusion of specific data.

Analysis of the primary efficacy variable will be repeated using the PPS.

Pharmacokinetic Per-Protocol Set:

The PK-PPS is a subset of the FAS, consisting of those subjects who had no important protocol deviations affecting the plasma concentration of UCB7665.

All analyses will be performed using SAS[®] version 9.3 or later (SAS Institute, Cary, NC, USA). Continuous variables will be summarized by visit (where applicable) with the statistics ineluding the number of subjects (n), mean, standard deviation (SD), median, minimum Categorical variables will be summarized by visit (where applicable). tion and any

The Treatment Groups for Dosing Period 1 will be as follows:

- Placebo •
- UCB7665 7mg/kg

e following For Dosing Period 2 and the Observation Period the following Treatment Groups will be considered for analysis:

- Placebo UCB7665 7mg/kg •
- Placebo UCB7665 4mg/kg
- UCB7665 7mg/kg UCB7665 7mg/kg
- UCB7665 7mg/kg UCB7665 4mg/kg

These Treatment Groups will be used for all safety and efficacy analyses.

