Descriptive statistics will be reported for all vital sign measurements (including pulse rate, systolic/diastolic BP, temperature, and respiratory rate). Measured values and changes from Baseline will be summarized by treatment group.

Physical and neurological examination findings and the results of any pregnancy testing will be presented in listings only.

Pharmacokinetic analysis 14.4.2

The PK variable is the plasma concentration of UCB7665. Pharmacokinetic parameters such as C_{max} and area under the curve will not be derived (eg, by non-compartmental analysis) due to the Stimited sampling performed at each visit.

Individual concentrations of UCB7665 will be listed and summarized at each scheduled time point. Descriptive statistics of concentrations will be calculated only if at least two thirds of the individual data points are quantifiable (≥lower limit of quantification [LLOQ]). Summaries will include the number of available observations, mean, median, SD, minimum, maximum, geometric mean, and geometric coefficient of variation (assuming log-normally distributed data). Values below the LLOQ will be reported with a clear sign indicating that they were below the LLOQ. Individual concentrations of UCB7665 will also be displayed graphically.

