2.2.2 Other and exploratory variables

2.2.2.1 Safety variables

The safety variables are the following:

- Occurrence of treatment-emergent adverse events (TEAEs)
- Vital sign values and changes from Baseline (systolic and diastolic BP, temperature, pulse rate, respiratory rate, and body weight) at each scheduled assessment during Treatment and Observation Periods
- 12-lead ECG values and change from Baseline at each scheduled assessment during Treatment and Observation Periods
- Laboratory values and changes from Baseline at each scheduled assessment during Treatment and Observation Periods (hematology, clinical chemistry, and urinalysis)
- Change from Baseline in exploratory safety biomarkers (may include but not limited to [REDACTED]) in subjects with severe headache and/or moderate to severe GI disturbance
- TEAEs leading to withdrawal of investigational medicinal product (IMP)

The clinical safety laboratory tests are detailed in [Table 11-1](#).

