3.3 Definition of Baseline values

Baseline will be the last available predose value prior to the first infusion of study drug in Dosing Period 1, or if missing, the Screening values. Scheduled or unscheduled measurements can be used as the Baseline value. Expected measurement-specific Baseline time points are presented in Table 3–1. If an unscheduled measurement occurs after the planned baseline measurement time point but before dosing, then the unscheduled measurement will be used.

Table 3–1: Expected Baseline Visits

Measurement	Baseline
Safety data 
 • Clinical Chemistry • Hematology • Urinalysis • ECG • Vital signs • [REDACTED] • [REDACTED] • [REDACTED] • Body weight 	
 • Clinical chemistry, Hematology, Urinalysis, ECG and Vital signs: Predose Day 1 or if missing the Screening value • [REDACTED] [REDACTED] [REDACTED]: Predose Day 1 • Body weight: screening visit

Table 3–1: Expected Baseline Visits

Measurement	Baseline
Pharmacodynamic data 
 Total serum IgG Serum IgG subclass concentrations MG specific antibodies (██████████) 	
 Total serum IgG and Serum IgG subclass: Predose Day 1 or if missing the Screening value Mg-specific autoantibodies: Predose Day 1
Immunological data: 
 IgM, IgE, IgA Serum complement levels (C3 and C4) and plasma complement levels (C3a and C5a) ██████████ Serum BAFF levels Cytokines ██████████ specific IgG antibodies Exploratory biomarkers relating to mechanism of action, disease activity, treatment response, and clinical outcome 	
 IgM, IgE, IgA, C3, C4, C3a, C5a, ██████████, BAFF, cytokines: Predose Day 1 ██████████ antibodies: Screening Exploratory biomarkers: Predose Day 1
Efficacy data: 
 QMG scale MG-composite scale MGADL MGFA scale MG muscle weakness Fatigue MGII SFEMG 	
 QMG, MG composite scale and MGFA: Predose Day 1 or if missing the Screening value MGADL, Muscle weakness, Fatigue scale, MGII, SFEMG: Predose Day 1.

██████████ BAFF=B-cell activating factor ; Ig=immunoglobulin; MGADL=myasthenia gravis-Activities of Daily Living; MGFA=Myasthenia Gravis Foundation of America; MGII= Myasthenia Gravis Impairment Index; SFEMG=single fiber electromyography; QMG=quantitative myasthenia gravis

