11.4 Vital signs, physical findings, and other observations related to safety

11.4.1 Vital signs

The following vital signs measurements will be obtained:

- Pulse rate
- Systolic and diastolic blood pressure
- Temperature (oral preferred, ear or axillary permitted)

- Respiratory rate

A by-subject listing of all vital sign measurements and change from Baseline will be presented by treatment group and time point. The listing will include a flag for values identified as TEMA/PCS as defined by the criteria outlined in [Table 14-7](#).

Descriptive statistics will be reported for all vital sign measurements. Measured values and changes from Baseline will be summarized by vital signs variables and time point for each treatment group. Summarization will be as treated, subjects who missed treatments will not be summarized.

Repeated and unscheduled measurements will be handled as described in [Section 4.3](#).

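### No analysis section specifies a by-group change-from-Baseline summary for body weight, a named safety variable, and the one sentence on its summary reads most naturally as pooled

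*SAP*

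**What the plan says.** The variable. SAP 2.2.2.1, repeating Protocol 4.2.1, lists as a safety variable "Vital sign values and changes from Baseline (systolic and diastolic BP, temperature, pulse rate, respiratory rate, and body weight", at each scheduled assessment. SAP Table 3-1 files weight under safety data and fixes its reference point: "Body weight: screening visit". According to Protocol 12.3.4, weight "will be determined at Screening (Visit 1), Visit 9, and at the FV (Visit 20").

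The grouping rule. Protocol 14.2 defines the Period 1 arms and the four sequences and states: "These Treatment Groups will be used for all safety and efficacy analyses". SAP 3.6 applies its group list to all analyses. That list adds two groups for subjects not dosed in Period 2.

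The analysis. SAP 11.4.1 opens with "The following vital signs measurements will be obtained" and lists pulse rate, systolic and diastolic blood pressure, temperature and respiratory rate. For these it promises: "Measured values and changes from Baseline will be summarized by vital signs variables and time point for each treatment group". Weight is taken up only in SAP 12: "Subject's body weight will be listed and summarized over all treatment groups". SAP 3.9, on changes to protocol-defined analyses, mentions only the MGADL model.

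**The concern.** A safety variable defined as a value and a change, with its own Baseline, should have a matching summary. Here the section that produces by-group changes does not include weight. The sentence that does include weight neither mentions change nor says that the groups are kept apart.

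Visit 9 is what is at stake. Weight is collected there before the first Period 2 infusion (Protocol 8.3.1), so Screening to Visit 9 compares three doses of UCB7665 with three of placebo under randomisation. Everyone dosed in Period 2 receives UCB7665, so the Final Visit offers no such comparison. Weight is a relevant variable in this study, because moderate to severe diarrhea and vomiting are adverse events of interest (Protocol 12.1.1.4; SAP 11.2).

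**Working it through.** The plan gives no figure to reproduce. The check is a comparison of the texts, followed by one line of arithmetic.

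**1. Where weight appears in the SAP, and what each place delivers**

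| Place | Content | Change from Baseline by group? |
|---|---|---|
| 2.2.2.1 | Named safety variable, value and change | Definition only |
| Table 3-1 | Screening is the Baseline | Definition only |
| 6.1 | Screening weight listed by group and summarised with demographics | No |
| 11.1 | Weight in the dosing listing | No |
| 11.4.1 | By-group values and changes for the listed vital signs | Weight not listed |
| 12 | Weight listed and summarised | Change not mentioned; grouping reads as pooled |

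No row specifies the summary that the definition calls for.

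**2. Where the omission begins.** Protocol 12.3.3 lists the vital signs without weight, and 12.3.4 treats weight separately. Protocol 14.4.1 reads: "Descriptive statistics will be reported for all vital sign measurements (including pulse rate, systolic/diastolic BP, temperature, and respiratory rate"). The parenthesis opens with a non-exhaustive word, so it does not exclude weight, but it does not name it either. SAP 11.4.1 follows this text.

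**3. Pooled or by group?** Where the SAP wants groups kept separate in the neighbouring safety summaries (11.3, 11.4.1, 11.4.2, 11.4.3), it says that the summary is by group or for each group. The weight sentence departs from that pattern, so pooled is the more natural reading. On either reading, change from Baseline is not mentioned.

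**4. What pooling would do at Visit 9.** Inputs: 1:1 allocation (Protocol 5.1) and an assumed mean weight change d on drug and 0 on placebo. The documents give no value for d.

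- Pooled mean change = (1/2) × d + (1/2) × 0 = d/2.
- For an assumed d = −1.0 kg, pooled = −1.0/2 = −0.5 kg. The between-group difference is −1.0 − 0 = −1.0 kg.

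The halving holds for any d when the arms are equal. It applies only if the pooled reading is right and change is derived at all.

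**The case against.** The strongest reply is that the SAP's defaults already cover weight. SAP 3.1 makes by-group output standard, with all-subjects output where stated. SAP 3.6 applies the groups to all analyses, and SAP 11 tabulates safety by period and group. The SAP 12 wording could loosely mean across each of the groups. In addition, SAP 1 falls back on the protocol wherever the SAP does not specify otherwise, and Protocol 14.4.1 summarises vital-sign changes by treatment group.

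Part of this stands. The sentence is ambiguous, so a reader who infers that no drug-versus-placebo weight change will be reported goes further than the text allows. The fallback does not settle the matter, though. SAP 12 does specify a weight summary, so its own wording governs the grouping. On change from Baseline, the protocol section it would fall back on does not name weight.

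Two other strong readings are not supported. A reader might conclude that the Screening weight is never used, but SAP 6.1 summarises it with demographics. A reader might also see an undeclared departure created by the SAP. SAP 3.9 is indeed silent on weight, but the omission already appears in Protocol 12.3.3 and 14.4.1.

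The practical loss is also limited. Weights are listed by subject, and the adverse events of interest are tabulated by group. The contrast is one visit in about 42 subjects (42/2 = 21 per arm). Its Baseline may precede the first dose by up to 28 days (Protocol 8.2.1).

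**Conclusion.** The gap is real and small. A named safety variable with a defined Baseline has no specified change-from-Baseline summary by treatment group. The one sentence on its post-Baseline summary most naturally means pooled and so conflicts with Protocol 14.2 and SAP 3.6. That there is no explicit by-group change summary does not depend on how the sentence is read. The loss of the Screening to Visit 9 comparison from the summaries does depend on the pooled reading, which is likelier but not certain. The 1.0 kg example is an assumption chosen to show the dilution; it is not an expected effect. This is descriptive safety reporting, and neither the primary analysis nor the collected data are affected.

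**What to change.** Add body weight to SAP 11.4.1, or replace the weight sentence in SAP 12, so that value and change from Screening are summarised by treatment group:

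- at Visit 9, for the two Period 1 arms;
- at the Final Visit, for the SAP 3.6 groups, including the two for subjects not dosed in Period 2.

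If weight is added to 11.4.1, the SAP 12 sentence should be deleted or reworded so that only one rule remains. An all-subjects column can be kept alongside the groups. The cost is one by-group descriptive table from data already scheduled for collection, with no new assessment and no change to any test.

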14.2 MG-composite score

The MG-composite score items and associated scores are provided in [Table 14–2](#). The total score is obtained by summing the responses to each individual item. Thus the score ranges from 0 to 50.

In the event of missing data at a particular time point, the MG-composite score will not be calculated. Due to the different weighting applied to each item it is not possible to impute the missing data with the average score across the remaining items.

Table 14–2: MG-composite score items and scoring algorithm

Item	Result/Grade	Result/Grade	Result/Grade	Result/Grade
Ptosis, upward gaze (physician examination)	>45 seconds/0	11-45 seconds/1	1-10 seconds/2	Immediate/3
Double vision on lateral gaze, left or right (physician examination)	>45 seconds/0	11-45 seconds/1	1-10 seconds/3	Immediate/4
Eye closure (physician examination)	Normal/0	Mild weakness (can be forced open with effort)/0	Moderate weakness (can be forced open easily)/1	Severe weakness (unable to keep eyes closed)/2
Talking (patient history)	Normal/0	Intermittent slurring or nasal speech/2	Constant slurring or nasal but can be understood/4	Difficult to understand speech/6
Chewing (patient history)	Normal/0	Fatigue with solid food/2	Fatigue with soft food/4	Gastric tube/6
Swallowing (patient history)	Normal/0	Rare episode of choking or trouble swallowing/2	Frequent trouble swallowing eg, necessitating changes in diet/5	Gastric tube/6
Breathing (thought to be caused by MG)	Normal/0	Shortness of breath with exertion/2	Shortness of breath at rest/4	Ventilator dependence/9

Item	Result/Grade	Result/Grade	Result/Grade	Result/Grade
Neck flexion or extension (weakest) (physician examination) ^a	Normal/0	Mild weakness/1	Moderate weakness (ie, 50% weak, +/-15%)/3	Severe weakness/4
Shoulder abduction (physician examination) ^a	Normal/0	Mild weakness/2	Moderate weakness (ie, 50% weak, +/-15%)/4	Severe weakness/5
Hip flexion (physician examination) ^a	Normal/0	Mild weakness/2	Moderate weakness (ie, 50% weak, +/-15%)/4	Severe weakness/5

^a Moderate weakness for head and neck items should be construed as weakness that equals roughly 50%+/-15% of expected normal strength. Any weakness milder than that would be mild and any weakness more severe than that would be classified as severe.

14.3 MG-Activities of Daily Living

The MGADL testing form is provided in [Table 14-3](#). The total score is obtained by summing the responses to each individual item. Thus the score ranges from 0 to 24.

[figure not shown]
In the event of missing data the following rules will be applied:

- If 1 or 2 items are not answered, the overall score will be obtained by imputing the missing items with the average score across the remaining items at the specific visit. The imputed value will be rounded to one decimal place
- If more than 2 items are missing the overall score will not be calculated

The following information (eg, questionnaire) is copyrighted and UCB does not have permission to disclose the contents.

This document cannot be used to support any marketing authorization application and any extensions or variations thereof.

REDACTED COPY

14.5 MG-Impairment Index

The MG-II is provided in [Table 14–6](#). The MGII can be summarized as a total score and also as 2 sub-scores reflecting an Ocular and a Generalized domain.

The total score is the raw sum of all the items, including the clinical examination and the patient-reported questionnaire.

The ocular score is calculated by summing 8 items reflecting ocular impairments. These items are: patient questionnaire items 1 to 6 and examination items 1 and 2.

The generalized score is calculated by adding items 7 to 22 from the patient questionnaire and items 3 to 6 from the examination.

For missing answers, impute the average score for the other items in the same domain or region (ocular, or generalized). Only calculate the total sum-score when there are ≤ 3 items missing.

The following information (eg, questionnaire) is copyrighted and UCB does not have permission to disclose the contents.

This document cannot be used to support any marketing authorization application and any extensions or variations thereof.

REDACTED COPY

14.6 TEMA/PCS criteria for Rozanolixizumab program

TEMA/PCS criteria for the clinical studies within the Rozanolixizumab clinical development program. These values are based on the CTCAE criteria version 4.03, grade 3 toxicity definitions and have been adapted to study needs.

Table 14-7: TEMA/PCS Values for Rozanolixizumab Clinical Development Program Based on CTCAE Grades

Domain	Term	Test	Criteria	Unit
Biochemistry	Hypoalbuminemia	Albumin	<2	g/dL
Biochemistry	Alkaline phosphatase increased	ALP	>5xULN	n/a
Biochemistry	Alanine aminotransferase increased	ALT	>5xULN	n/a
Biochemistry	Serum Amylase increased	Amylase	>2xULN	n/a
Biochemistry	Aspartate aminotransferase increased	AST	>5xULN	n/a
Biochemistry	Blood bilirubin increased	Bilirubin	>3 x ULN	n/a
Biochemistry	Hypercalcemia	Calcium	corrected >13.5 (>3.1); ionized (>1.8)	mg/dL (mmol/L)
Biochemistry	Hypocalcemia	Calcium	corrected <7 (<1.75); ionized (<0.9)	mg/dL (mmol/L)
Biochemistry	Cholesterol high	Cholesterol	>400 (>10.34)	mg/dL (mmol/L)
Biochemistry	Creatine phosphokinase increased	CK	>5xULN	n/a
Biochemistry	Creatinine increased	Creatinine	>3x baseline or >3 x ULN	n/a
Biochemistry	Acute kidney injury	Creatinine	>3x baseline or >4 x ULN	n/a
Biochemistry	Chronic kidney disease	eGFR or CrCl	<=29	ml/min/1.73 m ²
Biochemistry	GGT increased	GGT	>5xULN	n/a
Biochemistry	Hyperglycemia	Glucose	>250 (>13.9)	mg/dL (mmol/L)

Table 14-7: TEMA/PCS Values for Rozanolixizumab Clinical Development Program Based on CTCAE Grades

Domain	Term	Test	Criteria	Unit
Biochemistry	Hypoglycemia	Glucose	<40 (<2.2)	mg/dL (mmol/L)
Biochemistry	Hypermagnesemia	Magnesium	>3 (>1.23)	mg/dL (mmol/L)
Biochemistry	Hypomagnesemia	Magnesium	<0.9 (<0.4)	mg/dL (mmol/L)
Biochemistry	Hypophosphatemia	Phosphate	<2 (0.6)	mg/dL (mmol/L)
Biochemistry	Hyperkalemia	Potassium	>6	mmol/L
Biochemistry	Hypokalemia	Potassium	<3	mmol/L
Biochemistry	Hypernatremia	Sodium	>155	mmol/L
Biochemistry	Hyponatremia	Sodium	<130	mmol/L
Biochemistry	Hypertriglyceridemia	Triglycerides	>500 (>5.7)	mg/dL (mmol/L)
Biochemistry	Hyperuricemia	Uric acid	n/a	n/a
Body parameters	Obesity	BMI	>=30	kg/m ²
ECG	QT corrected interval prolonged (Bazett)	QTcB	>=501 ms OR increase >=60 ms compared to Baseline	ms
ECG	QT corrected interval prolonged (Fridericia)	QTcF	>=501 ms OR increase >=60 ms compared to Baseline	ms
ECG	PR prolongation	PR	>=210 ms AND >=10 ms change from Baseline	ms
Haematology	Anaemia	Hemoglobin	<8 (<4.9)	g/dL (mmol/L)
Haematology	Haemoglobin increased	Hemoglobin	increase >4 over ULN or increase >4 above Baseline (if Baseline is above ULN)	mg/dL
Haematology	Lymphocyte count decreased	Lymphocytes	<500 (<0.5)	/mm ³ (10 ⁹ /L)
Haematology	Lymphocyte count increased	Lymphocytes	>20,000 (>20)	/mm ³ (10 ⁹ /L)
Haematology	Neutrophil count decreased	Neutrophils	<1000 (<1)	/mm ³ (10 ⁹ /L)

Table 14-7: TEMA/PCS Values for Rozanolixizumab Clinical Development Program Based on CTCAE Grades

Domain	Term	Test	Criteria	Unit
Haematology	Platelet count decreased	Platelets	<50,000 (<50)	/mm ³ (10 ⁹ /L)
Haematology	Leukocytosis	WBC	>20,000	/mm ³
Haematology	White blood cell decreased	WBC	<2000 (<2)	/mm ³ (10 ⁹ /L)
Haematology	Monocytes increased	Monocytes	>2000 (>2)	/mm ³ (10 ⁹ /L)
Vital Signs	Hypertension	Blood pressure systolic	≥180 and an increase from Baseline of ≥15	mmHg
Vital Signs	Hypertension	Blood pressure diastolic	>105 and an increase from Baseline of ≥15	mmHg
Vital Signs	Hypotension	Blood pressure systolic	≤90 and a decrease from Baseline of ≥20	mmHg
Vital Signs	Hypotension	Blood pressure diastolic	<50 and a decrease from Baseline of ≥15	mmHg

This document cannot be used to support any marketing authorization applications or variations thereof.

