11.3 Clinical laboratory evaluations

Laboratory data (chemistry, hematology and urinalysis) and changes from Baseline (if applicable) for numeric variables will be summarized by treatment group and time point. Any laboratory measurements that are BLQ or ALQ will be handled as described in Section 4.2.2. Values outside the reference range for the numeric variables will be flagged in the listings. The reference ranges will also be reported in the listings. In addition, the listings will include a flag for values identified as treatment-emergent markedly abnormal (TEMA)/potentially clinically significant (PCS) as defined by the criteria outlined in Table 14-7.

Chemistry, hematology and coagulation parameters will be summarized by treatment group at each time point, for both absolute values and changes from Baseline.

The laboratory variables are presented in Table 11–1. For selected laboratory variables that are identified in Table 11–1, the change in category from Baseline will be presented in shift tables at each post-Baseline assessment.

Table 11–1: Clinical laboratory measurements

Category	Panel	Variable
Hematology	Red blood cell	RBC count, hemoglobin, hematocrit, HbA1c
	Platelet	Platelet count ^a
	White blood cell	WBC count
	White blood cell differential	Absolute counts: ANC, basophils, eosinophils, ALC, monocytes Percentages: neutrophils/leukocytes, basophils/leukocytes, eosinophils/leukocytes, lymphocytes/leukocytes, monocytes/leukocytes
Chemistry	Electrolytes	Sodium, chloride, potassium, calcium, phosphate, magnesium
	Enzymes	Amylase, Creatine kinase
	Hormones	procalcitonin
	Kidney function	Urea-N, creatinine ^a
	Proteins	Total protein, albumin ^a , alpha- and beta- globulins, hsCRP ^a
	Liver function	AST ^a , ALT ^a , GGT, ALP, LDH, total bilirubin, direct bilirubin (if indicated)

Table 11–1: Clinical laboratory measurements

Category	Panel	Variable
	Lipids	Total cholesterol, LDL cholesterol, HDL cholesterol, triglycerides
Urinalysis	Dipstick	pH, protein, glucose, ketones, urobilinogen, bilirubin, blood, nitrite, leucocytes
	Quantitative	Albumin, creatinine, protein
	Sediment	Leukocytes

^a Shift table will be created for these variables

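### SAP Table 14-7 gives the haemoglobin-increase limit in mg/dL but the anaemia limit in g/dL, so the listing flag as written is 1000 times too sensitive

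*SAP*

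**What the plan says.** SAP 14.6 introduces Table 14-7 as the criteria for markedly abnormal or potentially clinically significant values (TEMA/PCS). It states their origin: "These values are based on the CTCAE criteria version 4.03, grade 3 toxicity definitions and have been adapted to study needs".

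The table has two rows for haemoglobin:

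- Anaemia: below 8, with 4.9 in brackets; unit g/dL, with mmol/L in brackets.
- Haemoglobin increased: "increase >4 over ULN or increase >4 above Baseline (if Baseline is above ULN"; unit mg/dL, with no second unit.

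No footnote or conversion explains the change of unit.

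SAP 11.3 says how the table is used: "the listings will include a flag for values identified as treatment-emergent markedly abnormal (TEMA)/potentially clinically significant (PCS". It asks for this on top of a separate flag for values outside the reference range, and the reference ranges are to be printed in the listings as well. Haemoglobin is among the variables covered; the red cell line of Table 11-1 reads "RBC count, hemoglobin, hematocrit, HbA1c".

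**The concern.** Two limits for one analyte in one table should be on one scale unless the document says otherwise. Here they differ by a factor of 1000, and the row with the odd unit is the one that detects increases. A limit of 4 mg/dL is far below any change in haemoglobin that a laboratory would usually report, so the row cannot pick out a marked abnormality, which is the stated purpose of the table.

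What is at stake is the usefulness of one flag in one safety listing. A reader of the listing would meet a markedly-abnormal mark on results that are barely out of range, and the same mark on a rise of several g/dL. There is also some risk of carry-over, because SAP 14.6 presents the criteria as serving the clinical studies of the whole development programme.

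**Working it through.** **Inputs from the documents.** Increase limit 4, unit mg/dL (SAP Table 14-7). Anaemia limit 8 g/dL, paired with 4.9 mmol/L (same table). Use as a listing flag (SAP 11.3).

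**Inputs assumed, not in the documents.** Reporting step of haemoglobin: 0.1 to 0.001 g/dL, with the upper limit of normal (ULN) given to the same precision. SD of haemoglobin between subjects: 0.8 to 1.3 g/dL. SD of change within a subject: 0.3 to 1.0 g/dL.

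**Step 1: which scale does the anaemia row use?** The pair 8 g/dL and 4.9 mmol/L gives 4.9 / 8 = 0.6125 mmol/L per g/dL. It implies a molar mass of 80 g/L / 0.0049 mol/L, about 16,300 g/mol. If the 8 were in mg/dL, the same pair would imply 0.08 / 0.0049, about 16 g/mol, which is impossible for a protein. The anaemia row is therefore consistent with itself in g/dL.

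**Step 2: convert the increase limit.**

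- As printed: 4 mg/dL / 1000 = 0.004 g/dL, or 0.004 × 0.6125 = 0.00245 mmol/L.
- Same numeral in the anaemia row's unit: 4 g/dL, or 4 × 0.6125 = 2.45 mmol/L.
- Ratio: 4 / 0.004 = 1000.

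**Step 3: what the printed limit flags above ULN.** The smallest possible excess over ULN is one reporting step.

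| Assumed step (g/dL) | Smallest excess (mg/dL) | Flagged at >4 mg/dL? |
|---|---|---|
| 0.1 | 100 | yes, from the first step |
| 0.01 | 10 | yes, from the first step |
| 0.001 | 1 | from the fifth step (0.005 g/dL) |

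The answer is nearly the same on a continuous scale. Assume a normal distribution with ULN at its 97.5th percentile. The share of above-ULN values that is flagged is [1 − Φ(1.96 + limit/SD)] / [1 − Φ(1.96)].

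- Limit 0.004 g/dL: 98.8% at SD 0.8, 99.1% at SD 1.0, 99.3% at SD 1.3.
- Limit 4 g/dL: below 0.001% at all three.

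**Step 4: the Baseline limb.** Take a subject whose Baseline is above ULN and whose haemoglobin does not truly change. The chance that a later value exceeds Baseline by more than the limit is 1 − Φ(limit/SD of change).

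- Limit 0.004 g/dL: 49.5% at SD 0.3, 49.7% at SD 0.5, 49.8% at SD 1.0.
- Limit 4 g/dL: about 0.003% at SD 1.0, and effectively zero at the smaller SDs.

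As printed, noise alone meets this limb about half the time.

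**The case against.** The strongest reply is that this is a label slip with little reach. Most of that reply stands.

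- **Narrow use.** SAP 11.3 applies the laboratory criteria only as a listing flag. It plans no table of flagged counts. Haemoglobin is not among the variables marked for a shift table in Table 11-1. This stands.
- **Nothing is concealed.** A reader might infer that the extra flags would hide a true safety signal. The documents do not support that. The listing shows the haemoglobin value and its reference range, and out-of-range values are flagged anyway. The numbers are also small. Protocol Table 5.1 schedules laboratory tests at 10 post-baseline visits, so 42 subjects give at most 42 × 10 = 420 results. If 1% to 5% of them exceeded ULN (an assumption), about 4 to 21 would be marked, few enough to read line by line. What is lost is the flag's power to discriminate.
- **Not literally every value.** A reader might also infer that every result above ULN is flagged. The criterion has its own limb for subjects whose Baseline is above ULN. If that limb replaces the ULN limb, their values that lie above ULN but not above Baseline go unflagged. The claim has to be practically any value, not every value.
- **Conditional.** The over-flagging occurs only if the unit is programmed as printed. A programmer who applies 4 to data held in g/dL gets a flag on the anaemia row's scale. That is true, but the SAP is the specification, and the result should not depend on someone departing from it.
- **Adapted values.** SAP 14.6 says that the CTCAE limits were adapted to study needs, so the unit might be deliberate. Nothing in the documents says so, and a limit of 0.004 g/dL would serve no purpose beside the out-of-range flag. The CTCAE text is not reproduced, so this point rests on the contradiction between the two rows and not on CTCAE.

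**Conclusion.** The concern holds as a unit inconsistency. The two haemoglobin rows of Table 14-7 differ by a factor of exactly 1000, and the row for increases is wrong as written. The conversion needs no assumption. That practically any value above ULN would be flagged rests on an assumed reporting step of 0.01 to 0.1 g/dL and on literal programming of the printed unit; even at 0.001 g/dL only the first four steps above ULN escape.

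The importance is low. The damage is a flag that largely duplicates the out-of-range flag. No planned calculation, summary or test in the SAP changes because of it.

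**What to change.** Change the unit cell of the haemoglobin-increased row in Table 14-7 from mg/dL to g/dL, to match the anaemia row, before the flag is programmed. An mmol/L equivalent is optional: several rows of the table carry one unit only, and on the table's own ratio the value would be about 2.45 mmol/L. If the listing is already programmed, check which unit the code uses.

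The cost is one table cell. SAP Section 1 calls for an amendment when analysis definitions are modified, so the correction should be recorded that way, alone or with other changes.
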